12.4. Methods of Analysis for Pharmacokinetic Endpoints for Part 1 (only)

The PK population with intensive blood sample collection will consist of a subset of 7 participants in Japanese cohort (7 of the 50 participants).

If a participant in the PK subset with intensive blood sample collection (7 of the 50 participants) discontinues the study before completing the 8-hour PK sampling period or requires dose reduction or samples not collected per protocol or laboratory manual, the participant may be replaced with one of the other enrolled participants. If this is not feasible, additional participants above the anticipated sample size of 50 may be enrolled to ensure adequate number of participants are available for intensive PK sampling.

The PK population with sparse blood sample collection will consist of 43 participants (43 of the approximately 50 participants in the Japanese cohort) and 50 participants (50 of the approximately 50 participants in the Chinese cohort).

MMF and HES plasma concentrations will be summarized using descriptive statistics (mean, standard deviation, median, minimum, and maximum), and the mean values with standard errors will be plotted over time both on a linear and a logarithmic scale (where applicable). The MMF and HES concentrations obtained through intensive blood sample collection will also be used to calculate the following PK parameters using noncompartmental methods.

The following PK parameters will be calculated:

- C_{\max}
- AUC_{last}
- T_{\max}
- $t_{1/2}$ (MMF only)
- Other PK parameters can be calculated if feasible (CL/F, Vz/F, T_{lag}).

Each of these PK parameters will be summarized using descriptive statistics (mean, standard deviation, geometric mean, 95% CI, coefficient of variation, median, minimum and maximum for AUC_{last} , C_{\max} , $t_{1/2}$, CL/F, Vz/F; median, minimum, and maximum for T_{\max} and T_{lag}).

These PK parameters will also be descriptively compared to PK parameters from non-Japanese participants in Study ALK8700-A301 with respect to ethnic sensitivity and results will be discussed in the Part 1 and 2 study reports.

MMF and HES plasma concentrations predose and at 2 to 3 hours postdose on Day 29 and Day 57 will be summarized using descriptive statistics (mean, standard deviation, geometric mean, 95% CI, coefficient of variation, median, minimum and maximum).

CONFIDENTIAL

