12.7. Sample Size Considerations

A sample size of approximately 50 participants per cohort is based on feasibility considerations and is deemed sufficient to characterize the safety and tolerability profile. With this sample size, the probability of observing at least 1 SAE with a background incidence of 4% would be 87% based on data from the 24-week Treatment Period in Study ALK8700-A301 (a DRF global Phase 3 study) in RRMS participants who were naïve to DRF treatment.

In addition, assuming the incidence of GI AEs at 24 weeks of 27.5% as observed in participants naïve to DRF treatment recruited in Study ALK8700-A301, the sample size of approximately 50 participants per cohort will provide a 96% probability of observing a point estimate of GI AE

CONFIDENTIAL

The information contained herein may not be used, disclosed, or published without the written consent of Biogen MA Inc.

incidence rate < 39% in Part 1 of the study (at 24 weeks). The 24-week incidence rate of 39% was observed in East Asian participants who received DMF twice daily in Study 109MS305.

Based on the observed DRF PK parameters in fasted participants from ALK8700-A103 study, CV of AUC (last) was estimated to be 30.9; therefore, a sample size of 7 Japanese participants would be needed to evaluate the MMF PK parameters with sufficient precision, which is defined as an evaluation of the PK parameters of MMF with at least 80% power to achieve a 95% CI within 60% to 140% of the geometric mean. Since the variability of HES parameters is significantly lower, the data from 7 participants will also provide a robust assessment of AUC_{last} and C_{max} of HES in Japanese MS participants.

The Sponsor may enroll fewer than 50 participants per cohort based on the observed recruitment rate in these regions.

CONFIDENTIAL

The information contained herein may not be used, disclosed, or published without the written consent of
Biogen MA Inc.

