5.8. Pharmacokinetic Endpoints

5.8.1. Pharmacokinetic Concentrations

The PK Analysis Set with intensive blood sample collection will consist of a subset of 7 participants in Japanese cohort.

The PK Analysis Set with sparse blood sample collection will consist of approximately 43 Japanese participants (total participants in the Japanese cohort except for the subset of participants enrolled in the intensive PK sample in which sparse PK samples are not being collected) and approximately 50 Chinese participants (total participants in the Chinese cohort).

Blood samples for PK analysis of metabolites MMF and HES will be collected at the following timepoints on any day [from Day 29 to Day 169] for intensive blood samples and on [Day 29 and Day 57] for sparse blood samples:

- Intensive blood sample collection on any day [from Day 29 to Day 169]: pre-dose (within 30 minutes), $0.5\pm5\text{min}$, $1\pm5\text{min}$, $2\pm15\text{min}$, $3\pm15\text{min}$, $4\pm15\text{min}$, $6\pm15\text{min}$, $8\pm15\text{min}$ hours post-dose

- Sparse blood sample collection on [Day 29 and Day 57]: pre-dose, 2 – 3 hours post-dose

MMF and HES plasma concentrations will be analyzed using the PK Analysis Set. The plasma concentrations will be presented separately for intensive and sparse subsets of data. The Plasma concentrations for sparse subsets of data will be presented by cohort. Additionally, the descriptive summary statistics and box plots will be constructed to descriptively compare MMF (post-dose) and HES (pre-dose and post dose) plasma concentrations between Japanese and Chinese participants of this study and all participants with sparse PK concentrations from ALK8700-A301.

The descriptive summary statistics will be provided by nominal sampling times of PK Study Day. Plots of individual concentrations over actual sampling time and mean concentrations (with SD/SE as error bars) over nominal sampling time will be presented both on a linear and semi-logarithmic scale for intensive subset of participants only. In addition, geometric mean concentrations (with 95% CI as error bars) over nominal sampling time will be presented both on a linear and semi-logarithmic scale for intensive subset of participants only.

LLOQ for plasma concentration of MMF and HES is 25 ng/mL and 50 ng/mL respectively.

PK parameters and/or timepoints with PK concentrations excluded from the PK analysis and summary statistics will be flagged and presented in listings.

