5.8.2. Pharmacokinetic Parameters

The MMF and HES concentrations collected based on intensive blood samples will also be used to calculate the following PK parameters:

Pharmacokinetic Parameter	Definition
C_{max}	Maximum observed concentration
T_{max}	Time to reach maximum observed concentration
AUC_{last}	Area under the concentration-time curve from time zero to time of the last quantifiable concentration
AUC_{tau}	Area under the concentration-time curve over the 12-hour dosing interval
$T_{1/2}$ (MMF only)	Terminal half-life
CL/F	Apparent total body clearance at steady-state, calculated as Dose / AUC_{tau} , assuming a systemic availability (F) of 1 for both metabolites
V_z/F	Apparent volume of distribution based on the terminal phase at steady-state (MMF only), calculated as Dose / ($\lambda_z * AUC_{tau}$), assuming F of 1 for the MMF metabolite
T_{lag}	Lag time
C_{12hr}	Imputed concentration at 12-hour postdose

The full details for derivation of PK parameters, handling of BLQ values and missing

concentration during NCA analysis are provided in the Pharmacokinetic Analysis Plan (PKAP).

All PK parameters will be summarized using descriptive statistics for intensive subset of data. For selected PK parameters, the descriptive summary statistics and box plots will be constructed to descriptively compare MMF and HES PK parameters between Japanese participants of this study and all participants with PK parameters from ALK8700-A301.

Additional PK parameters may be summarized if appropriate.

The records excluded from summary statistics will be flagged and presented in the listings. MMF and HES PK parameters for all participants will be listed.

The diagnostic statistics for PK parameters from regression analysis which are outlined in the PKAP will be provided in the listings.

The geometric mean, geometric CV%, 95% CI will be calculated assuming data follows lognormal distribution. Parameter estimates calculated from natural log transformed data will be exponentiated to obtain estimates on the original lognormal data.

6. Changes from Protocol-Specified Analyses

Not Applicable

7. Summary of Changes from the Previous Version of the SAP

Not Applicable

8. References

Not Applicable

APPENDICES

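### The ethnic-sensitivity PK comparison with Study ALK8700-A301 is planned as side-by-side summaries and box plots, with no between-population ratio or interval; this matters most for MMF

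*SAP*

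**What the plan says.** Protocol 12.4 gives the purpose for the intensive-sampling parameters: "These PK parameters will also be descriptively compared to PK parameters from non-Japanese participants in Study ALK8700-A301 with respect to ethnic sensitivity". SAP 5.8.2 carries this out, for selected parameters, as follows: "the descriptive summary statistics and box plots will be constructed to descriptively compare MMF and HES PK parameters between Japanese participants of this study". The other side of that comparison is every A301 participant who has PK parameters. SAP 5.8.1 does likewise for the sparse samples: "box plots will be constructed to descriptively compare MMF (post-dose) and HES (pre-dose and post dose) plasma concentrations between Japanese and Chinese participants". Here too the A301 side is everyone in that study with sparse concentrations. Protocol 12.4 describes the Japanese sparse comparison as tables and graphics.

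The intensive set is small: "The PK Analysis Set with intensive blood sample collection will consist of a subset of 7 participants in Japanese cohort". The sparse set is about 43 Japanese and about 50 Chinese participants.

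Within each group the SAP works on the log scale: "The geometric mean, geometric CV%, 95% CI will be calculated assuming data follows lognormal distribution". SAP 5.1.1 also allows two-sided 95% CIs for selected PK parameters. Neither document specifies a ratio between populations, an interval for such a ratio, or a criterion for calling exposures similar.

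The number 7 is justified in protocol 12.7 (repeated in SAP 2.3) by "CV of AUC (last) was estimated to be 30.9" and a target of "at least 80% power to achieve a 95% CI within 60% to 140% of the geometric mean". HES is covered by the remark "Since the variability of HES parameters is significantly lower", without a figure.

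Protocol 12.4 also plans a population PK analysis of integrated concentration data for ethnic sensitivity in HES, to be reported separately. The visible SAP text does not mention it.

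**The concern.** Whether exposure differs between populations is a question about a ratio. The plan log-transforms the data and estimates each group's geometric mean, but stops short of the ratio and its interval. A box plot cannot stand in for them: its width reflects variation between people and does not shrink towards zero as data accumulate, so overlap or separation of boxes does not tell a reader which differences the data rule out.

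The PK results are secondary endpoints and feed the Part 1 interim analysis that SAP 4.1 plans for Japanese regulatory interaction. MMF is the active metabolite and the basis of the PK bridge to DMF (protocol 3.2.3). For MMF, the comparisons in SAP 5.8.1 and 5.8.2 are the only ethnic comparisons that the documents name.

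The comparator is also described in two ways. Protocol 12.4 takes the non-Japanese participants of A301 for the intensive parameters; SAP 5.8.2 takes all participants. SAP Section 6 records no change from the protocol.

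**Working it through.** **Inputs.** Japanese intensive n = 7 (SAP 5.8.1). CV of MMF AUC_last = 30.9, read as a percentage (protocol 12.7). Number of A301 participants with PK parameters: not given, so assumed, mainly 12 to 100. The same CV is assumed in both groups.

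**Log-scale SD.** sqrt(ln(1 + 0.309²)) = 0.302.

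**Step 1: the plan's own figure.** The probability that the 95% half-width on the log scale is at most ln 1.4 = 0.3365 is the chi-square probability, on n − 1 df, of falling below n(n − 1) × [0.3365 / (t × 0.302)]², with t the 0.975 quantile on n − 1 df.

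- n = 6: t = 2.571, 30 × (0.3365/0.776)² = 5.64, probability 65.7%.
- n = 7: t = 2.447, 42 × (0.3365/0.739)² = 8.71, probability 80.9%.

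So 7 is the smallest number that reaches 80%, as stated. The calculation involves only the Japanese group; no comparator enters it.

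**Step 2: precision of the comparison.** The 90% CI is the estimated ratio multiplied and divided by exp[t(0.95, 5 + m) × 0.302 × sqrt(1/7 + 1/m)], where m is the A301 number.

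| m (assumed) | SE (log) | t | 90% factor | interval if the estimate is 1.00 |
|---|---|---|---|---|
| 12 | 0.144 | 1.740 | 1.28 | 0.78 to 1.28 |
| 20 | 0.133 | 1.708 | 1.25 | 0.80 to 1.25 |
| 35 | 0.125 | 1.684 | 1.23 | 0.81 to 1.23 |
| 100 | 0.118 | 1.659 | 1.22 | 0.82 to 1.22 |
| very large | 0.114 | 1.645 | 1.21 | 0.83 to 1.21 |

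The last row shows that the 7 Japanese participants set the limit: more A301 data cannot bring the factor below about 1.21.

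**Step 3: sparse samples.** The same formula with 43 Japanese, t on 41 + m df and an assumed A301 number of 50 to 500 gives 90% factors of 1.11 to 1.08 at CV 30.9% (log SD 0.302), 1.21 to 1.16 at CV 60% (0.555) and 1.33 to 1.24 at CV 100% (0.833). The documents give no CV for the sparse concentrations, so all three are illustrations. Depending on that CV, the sparse ratio could be more precise than the intensive one.

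**Step 4: feasibility on the log scale.** SAP 5.1.6 sets concentrations below quantification to zero for descriptive statistics. The log of zero is undefined, so a ratio of sparse concentrations needs its own rule for such values. SAP 5.8.1 gives the quantification limits as 25 ng/mL for MMF and 50 ng/mL for HES.

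**The case against.** The other side has real weight. The protocol chose a descriptive comparison, the secondary objective is to evaluate the PK of MMF and HES, and the sample size meets its own stated target. Per-group geometric means and 95% CIs are planned; if the A301 summaries carry the same statistics, a reader could work out a ratio and an approximate interval. A301 is a separate study, so any ratio mixes ethnicity with other differences between the studies. The documents set no similarity bounds, so the interval would serve no decision rule. All of this stands. It argues for labelling the ratio carefully and for treating its absence as a reporting gap, but not for leaving it out.

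Two stronger readings are tempting, and the documents do not support them.

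- **A reader might infer that the whole ethnic assessment rests on box plots of 7 people.** It does not. Protocol 12.4 plans a population PK analysis of HES ethnic sensitivity using all concentrations from this study, and the sparse comparison adds about 43 Japanese and 50 Chinese participants. Whether the population PK report will give an ethnicity effect with an interval cannot be checked from these documents.
- **A reader might infer that a 25% to 30% exposure difference would usually be hidden by overlapping boxes.** In simulation at CV 30.9% with 12 to 100 A301 participants, the interquartile boxes do overlap in 76% to 85% of studies at a true ratio of 1.25 and 68% to 77% at 1.30. But this applies to increases in MMF AUC_last. At a ratio of 0.70 overlap is about 50%, and at an assumed HES CV of 20% it is about 40% at 1.30. Overlap at 1.25 also rises as A301 participants are added (76%, 82% and 85% with 12, 35 and 100), so it does not measure a shortage of information. Nothing in the plan makes overlap a criterion.

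**Conclusion.** The point holds for the intensive noncompartmental parameters and the sparse concentrations: the comparison made for ethnic sensitivity has no planned ratio or interval. It matters most for MMF, for which no population PK assessment of ethnicity is named. The intensive MMF AUC_last ratio would carry a 90% CI of about ×/÷1.28 to ×/÷1.22, so an estimate of 1.00 would be compatible with true ratios from about 0.78 to 1.28 (A301 n = 12) or 0.82 to 1.22 (n = 100). The plan as written does not show this.

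These figures rest on the A103 CV applying to both groups, on lognormal data and on the assumed A301 numbers. They do not cover C_max or HES, for which no CV is given. The sample size of 7 is correct for its stated purpose. This is an inexpensive improvement to a descriptive secondary analysis and leaves the primary safety conclusions untouched.

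**What to change.** - **SAP 5.8.2:** for AUC_last and C_max of MMF and HES, report the geometric mean ratio (Japanese : A301 comparator) with a 90% CI from the difference of log means.
- **SAP 5.8.1:** do the same for sparse postdose MMF and for predose and postdose HES, for each cohort against the A301 comparator, with a stated rule for values below quantification on the log scale.
- **Comparator:** define it as one group, reconciling the non-Japanese participants of protocol 12.4 with the all-participants wording of SAP 5.8.2. If the SAP's choice stands, record it in SAP Section 6.
- **Labelling:** state that each ratio is a descriptive cross-study estimate and that 7 was not sized for the comparison.
- **Cross-reference:** point to the population PK analysis of HES in protocol 12.4 and its separate report.
- Keep the box plots as supporting displays.

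The cost is a few lines of SAP text and one table, from data already needed for the box plots. The downside is that the intensive-PK intervals will be visibly wide; the ratio displays that imprecision but does not reduce it.

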9.3. Pharmacokinetic Assessments

The subset of 7 Japanese participants must be in the overnight fasted state (10 hours) prior to administration of the dose of DRF on study Day 29, and no food will be allowed for at least 4 hours after the dose of DRF. Participants will be allowed water ad libitum, except for 1 hour before and 2 hours after administration of the dose of DRF.

For the subset of 7 Japanese participants with intensive blood sample collection for PK analysis of metabolites MMF and HES, samples will be obtained at the following:

- -30 to 0 minutes (predose) and at 0.5, 1, 2, 3, 4, 6, and 8 hours (postdose)
- For intensive PK sampling for MMF and HES, noncompartmental plasma PK parameters (AUC_{last} , C_{max} , t_{max} , and $t_{1/2}$ [MMF only]) will be calculated. The PK parameters (AUC_{last} , C_{max} , t_{max}) for MMF and HES in Study 272MS303 will be compared with those in Study ALK8700-A301.

CONFIDENTIAL

The information contained herein may not be used, disclosed, or published without the written consent of Biogen MA Inc.

In addition, sparse blood samples will be collected for PK analysis of the metabolites MMF and HES as follows:

- On Day 29, blood samples will be collected -30 to 0 minutes (predose) and 2 to 3 hours (postdose) for participants with sparse blood sample collection (approximately 43 per Japanese cohort and 50 per Chinese cohort).
- On Day 57, blood samples will be collected -30 to 0 minutes (predose) and 2 to 3 hours (postdose) for all participants with sparse blood sample collection (approximately 50 per cohort).
- Participation in the sparse PK cohort does not preclude enrollment in the intensive PK cohort as well. In the event that a participant is enrolled in both the sparse and intensive PK cohorts and intensive PK sampling was completed on Day 29 or Day 57 for a participant, sparse PK sampling will not be required for said days. However, if it is determined that intensive PK is not feasible by Day 57, sparse PK sampling will be completed according to protocol and intensive PK should be completed at later visits.

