The information contained herein may not be used, disclosed, or published without the written consent of Biogen MA Inc.

The plasma concentrations in 43 Japanese participants will be compared with those in Study ALK8700-A301 using tabular data and graphics. These results will be discussed in study reports for Parts 1 and 2.

Population PK analysis will be performed by using integrated plasma concentration data, including all plasma concentration data from Study 272MS303, to assess ethnic sensitivity in terms of HES PK. Detailed population PK analysis will be described in a separate report.

Table 6: Pharmacokinetic Analysis Timepoints

	Intensive PK Timepoints ¹							
	Predose	0.5 h	1 h	2 h	3 h	4 h	6 h	8 h postdose
Time Window	-30 to 0 min	±5 min	±5 min	±15 min				

¹ PK analysis will be performed in a subset of 7 participants in the Japanese cohort at any timepoint in the period between Week 4 (Day 29, Visit 3 ± 3 days) and Week 24 (Day 169, Visit 8 ± 5 days), both inclusive. If a participant from the PK subset population discontinues the study during the specimen sampling period, then the participant may be replaced with one of the enrolled participants.

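### SAP 5.8.2 compares the Japanese PK parameters with all A301 participants, Protocol 12.4 specifies non-Japanese A301 participants, and SAP Section 6 records no change

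*SAP*

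**What the plan says.** Protocol 12.4, the statistical methods section for PK, states that the noncompartmental parameters from intensive sampling will be "descriptively compared to PK parameters from non-Japanese participants in Study ALK8700-A301 with respect to ethnic sensitivity". This sentence gives both the comparator and the purpose.

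Protocol 9.3 describes the same comparison more loosely: AUClast, Cmax and tmax "for MMF and HES in Study 272MS303 will be compared with those in Study ALK8700-A301". No ethnic group is named there.

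SAP 5.8.2 plans summary statistics and box plots for selected parameters, setting this study's Japanese participants against "all participants with PK parameters from ALK8700-A301". SAP Section 6, "Changes from Protocol-Specified Analyses", is marked as not applicable. SAP Section 1 says the plan was developed from Protocol Amendment 4.

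The sparse samples are a separate matter. Protocol 12.4 says: "The plasma concentrations in 43 Japanese participants will be compared with those in Study ALK8700-A301 using tabular data and graphics". SAP 5.8.1 compares the Japanese and Chinese participants with "all participants with sparse PK concentrations from ALK8700-A301". Neither text restricts the A301 side by ethnicity.

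**The concern.** A comparison meant to show whether Japanese participants differ from others needs a comparator without Japanese participants. Protocol 12.4 builds that in. SAP 5.8.2 does not leave the comparator open; it replaces the restricted group with everyone. If Japanese participants contributed PK data to A301, the reference group would contain part of the group under test, and any true difference would look somewhat smaller than it is.

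The stake is modest but not empty. MMF is the active metabolite (Protocol Section 3). The population PK analysis in Protocol 12.4 is assigned ethnic sensitivity for HES only. For MMF parameters, this descriptive comparison is therefore the only ethnic-sensitivity assessment that the two documents name. SAP 4.1 also puts the secondary endpoints, which are the PK endpoints, into the Part 1 interim analysis for regulatory interaction in Japan. A change of comparator there should be visible, and Section 6 is where a reader would look for it.

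**Working it through.** **1. The texts side by side**

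| Place | Data | A301 comparator |
|---|---|---|
| Protocol 12.4 | PK parameters | Non-Japanese participants |
| Protocol 9.3 | PK parameters | A301, no restriction stated |
| SAP 5.8.2 | PK parameters | All with PK parameters |
| Protocol 12.4 | Sparse concentrations | A301, no restriction stated |
| SAP 5.8.1 | Sparse concentrations | All with sparse concentrations |
| SAP Section 6 | Changes from protocol | None listed |

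SAP 5.8.2 is compatible with Protocol 9.3 but not with 12.4. Protocol 9.3 can be read consistently with 12.4, because it does not define the A301 group. SAP 5.8.2 cannot, because it says all.

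**2. The plan's own PK figure**

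Inputs from Protocol 12.7 and SAP 2.3: CV of MMF AUClast 30.9 (read as percent); n = 7; at least 80% power for a 95% CI within 60% to 140% of the geometric mean.

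- Log-scale SD: σ = √ln(1 + 0.309²) = 0.302.
- The upper limit binds, since ln 1.4 = 0.336 is smaller than |ln 0.6| = 0.511. The CI meets the criterion when s ≤ s_max = ln(1.4) × √n / t(0.975, n−1).
- At n = 7: s_max = 0.336 × 2.646 / 2.447 = 0.364, and (n−1)(s_max/σ)² = 6 × (0.364/0.302)² = 8.7. The chi-square probability on 6 df is 80.9%.
- At n = 6 the probability is 65.7%.

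So 7 is the smallest n that meets the criterion, and the stated figure is reproduced. Changing the A301 comparator does not affect it.

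**3. Possible shrinkage of the contrast**

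Let R be the true Japanese to non-Japanese geometric mean ratio and f the Japanese share of the A301 PK participants. Assume Japanese participants in A301 have the same geometric mean as those in this study. The geometric mean of the pooled A301 group is then R^f times that of the non-Japanese, so the observed ratio is R / R^f = R^(1−f). Neither R nor f is in the documents. The values below are assumptions.

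| f | R = 1.20 | R = 1.25 | R = 1.50 |
|---|---|---|---|
| 0% | 1.200 | 1.250 | 1.500 |
| 1% | 1.198 | 1.247 | 1.494 |
| 5% | 1.189 | 1.236 | 1.470 |
| 10% | 1.178 | 1.222 | 1.440 |
| 20% | 1.157 | 1.195 | 1.383 |

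**4. Against sampling error**

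With n = 7 and σ = 0.302, the typical 95% half-width on the log scale is 2.447 × 0.302 / √7 = 0.279. That is a CI from 76% to 132% of the geometric mean for the Japanese side alone. The log-scale shrinkage is f × ln R. For R = 1.25 (ln R = 0.223) it is 0.011 at 5%, 0.022 at 10% and 0.045 at 20%. These are 4%, 8% and 16% of the half-width.

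**The case against.** The strongest reply is that the mismatch may have no content. No text says that any Japanese participant gave PK data in A301, and Protocol 3.1.1 describes DRF data in Asian populations only as limited. If there were none, Section 6 omits nothing of substance. The SAP also agrees with Protocol 9.3, so it follows one of two protocol wordings. The comparison is descriptive, with no planned between-study ratio, test, margin or decision rule. Ethnic sensitivity for HES also goes to a separate population PK analysis.

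Most of this stands, and it sets the severity. It does not remove the mismatch. Protocol 12.4 is the more specific text and the only one that states the purpose, and neither document shows that the Japanese share is zero.

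A reader might infer more than the documents support:

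- That the contrast is in fact diluted. This needs Japanese participants in the A301 PK data, which is not shown.
- That the same people would be on both sides. The Japanese side is limited to this study, and exclusion criterion 23 bars previous participation in DRF studies. At most the same ethnic group would appear in both.
- That SAP 5.8.1 also departs from the protocol. The protocol sets no ethnic restriction for sparse concentrations.
- That this is the main bridging analysis, or that the wording was chosen to favour similarity. PK is a secondary objective, Protocol 3.2.3 uses the bridging term for DRF against DMF, and nothing in the documents speaks to motive.

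**Conclusion.** SAP 5.8.2 does not match Protocol 12.4 on the A301 comparator for PK parameters, and SAP Section 6 does not record the difference. That rests on the wording alone and needs no assumption.

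The effect on results is conditional. It is nil if the A301 PK data contain no Japanese participants. It is small if they form a minor share: an assumed ratio of 1.25 becomes 1.24 at 5%, 1.22 at 10% and 1.20 at 20%, always toward 1 and well inside the sampling error of 7 participants. These figures depend on the assumed R and f and on equal exposure in Japanese participants of the two studies. Severity is low: a consistency correction to a descriptive comparison, not a demonstrated bias.

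**What to change.** In SAP 5.8.2, define the A301 comparator as non-Japanese participants with PK parameters, as in Protocol 12.4, and report how many Japanese participants that excludes. If the number is zero, say so; the two sets then coincide. If the sponsor prefers to keep all A301 participants, record the change and its reason in SAP Section 6 and still give the number of Japanese participants included. Align the wording of Protocol 9.3 with 12.4.

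The same filter could be applied to the Japanese sparse-concentration comparison in SAP 5.8.1. That is an optional step for consistency, not the correction of a protocol departure.

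The cost is one filter on existing A301 data and a few words in each document. Sample size, power and data collection do not change.
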